## Study Protocol

### Description of the Study

In the United States, hypertension (HTN) is the leading risk factor for cardiovascular disease and a more significant problem among Black women. About 46.1% of Black women over the age of 20 have HTN compared to White (30.1%) and Hispanic (29.9%) women. Currently, the prevalence of HTN in Black women is highest in the United States and is expected to increase underscoring the relatively ineffective prevention and management efforts for blood pressure (BP) control. Black adults tend to develop HTN earlier in life with greater severity and more organ damage when compared to Whites and uncontrolled HTN increases the risk of heart failure, myocardial infarction, stroke, and kidney disease. Black females experience a substantially higher death rate from HTN at 2.1 times the rate of both White and Hispanic females. Poor execution of evidence based HTN guidelines and clinical inertia among healthcare providers along with patient nonadherence to prescribed treatment contribute to poor BP control. It is well known that antihypertensive medications along with lifestyle modifications have proven efficacy in lowering BP when adhered to consistently. However, for Black adults, the lingering effects of their historical legacy, continued segregated communities, high poverty rates, and unequal medical treatment, place them in a unique position to view healthcare with skepticism that differs from all other racial/ethnic groups. Thus, accepted approaches to HTN management have not been optimally effective in producing sustained BP control for Black women. Since nonadherence occurs in the context of everyday living, strategies are needed that encourage more active individual engagement in health care behaviors and self-care activities, in the physical and social environment where patients can perform them independently. This research study evaluated community-based interventions designed to control hypertension using interactive self-care strategies with coaching and technology.

This study includes a sample of community dwelling Black women with uncontrolled HTN. All participants meeting study eligibility requirements will receive the Chronic Disease Self-Management Program (CDSMP) workshop for 6 weeks. Participants from this pool will be randomized to the treatment and control arm. All study participants will continue to receive usual care for their HTN.

The intervention will be divided into three steps. At Step 1 for 3 months, the treatment arm will receive electronic monitoring (of participants' BP, weight, physical activity, food diary, and medication-taking) with weekly Interactive Technology Enhanced Coaching (ITEC) while the control arm will receive usual care with manual BP measurements monthly. At Step 2 for three months, the treatment arm will receive electronic monitoring with ITEC biweekly, and the control arm will receive electronic monitoring only. At Step 3 for three months, both the treatment arm and the control arm will receive electronic monitoring only.

Information from this study may be used to enhance self-care management, control blood pressure, and increase the quality of life for Black women who are burdened with the adverse effects of HTN and its high disability and mortality rates.

Our sample of n=45 participants per arm (N=90 in total), will be measured (electronic measurements, anthropometric measurements, and data collection tools) at baseline, 3 months, 6

months, and at 9 months post CDSMP. A hierarchical, mixed-effects repeated measures design will be used to analyze the data.

## **Objective**

The specific aims for this study evaluated the effectiveness of an established Chronic Disease Self-Management Program (CDSMP) plus an interactive technology-enhanced coaching (ITEC) intervention on improving 1) BP control, and 2) medication adherence and lifestyle modifications (physical activity, diet, and weight management) compared to the CDSMP and interactive technology (IT) alone.

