## **Design**

The proposed project is a two-arm randomized controlled trial (RCT), repeated measures design. We hypothesized that participants who received the CDSMP and ITEC would have lower systolic/diastolic BP and better adherence to antihypertensive medication(s) and lifestyle recommendations post intervention compared to participants receiving the CDSMP and IT alone. Measurements were obtained over 9 months post CDSMP.

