## Baseline and Repeated Measures

**Manual Blood Pressure.** Using a home BP monitoring procedure (Muntner et al., 2019), participants were seated quietly for at least 5 minutes with their back supported and feet flat on the floor. A manual BP measurement was taken with a Welch Allyn Tycos (DS58) hand aneroid sphygmomanometer in the bare left upper arm while supported at heart level. Three consecutive BP measurements were taken, one minute apart and averaged (Pickering et al., 2005; Whelton et al., 2018). Manual BP measurements were taken at baseline and then at month 3, 6, and 9 to verify readings from the digital Omron oscillometric BP monitor used for the technological data in the study (Abel & DeHaven, 2021). To maintain consistency with the Omron BP recommendation, the left upper arm was used for BP measurements (Omron Healthcare, 2015a).

**Body Mass Index.** A portable platform Seca 813 electronic scale was used to measure weight in pounds. Height was measured using a portable Seca 217 stadiometer with measurements to the nearest 0.1 centimeter. Weight and height data were used to calculate the body mass index (BMI) using the metric system formula, weight in kilograms divided by height in meters squared, expressed as: weight (kg) / [height (m)] (*Healthy weight: Body mass index*, 2015).

**Waist Circumference.** Waist circumference was measured to the nearest 0.1 cm. by using a soft Gulick tape measure to circle around the waist at the top of the iliac crest and slightly above the level of the umbilicus from the “0” end of the tape to the intersection of the waist measurement number. The Gulick tape measure includes a mechanism to ensure consistent tension when measuring. The participant stood in an upright position without sucking the abdomen in while the tape was pulled taut without squeezing into the skin (Frey, 2019, September, 2; "Waist measurement," n.d.).

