## Technology

After completing the CDSMP sessions, study participants were randomly assigned to either the treatment (ITEC) or the control arm (IT).

The technology component of the study was linked to Fitbit Plus, a cloud-based collaborative care platform that was designed to store and track data. The PI was trained in the Fitbit Plus platform, synchronizing data collection devices, instructing participants in the use of equipment, monitoring participant data, and interactive coaching messages. In the privacy of their homes, or another preferred location, each study participant received individualized instruction (about 45 to 90 minutes) to Fitbit Plus and all study tools accommodating various technological skills.

Study equipment included three wireless tools (Omron BP monitor, Fitbit activity tracker, and Fitbit weight scale) and five apps (Omron Connect, Fitbit, MyFitnessPal, Apple Health if iPhone user or Google Fit if android user, and Fitbit Plus). Apps were installed and tools synchronized to the participant’s smartphone. Apple Health and Google Fit allowed Fitbit Plus to import app data from Fitbit, MyFitnessPal, and Omron. Participant action plans were set up in Fitbit Plus to correspond to the study aims. As participants wore their Fitbit activity tracker, took their BP, stepped onto the weight scale, or entered food intake, their measurement data were transmitted in real time via Wi-Fi and Bluetooth Smart technology to the Fitbit Plus dashboard. In the dashboard, participants could view their data along with the PI. Two exceptions were the manual BP recording for Android users and the manual self-reported medication-taking for all participants, as described under Fitbit Plus Measures. The PI monitored all study participant data during a two-week trial period to allow participants an opportunity to adapt to using the wireless tools and apps. Once the orientation period was over, data were monitored via the Fitbit Plus platform for study purposes.

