### Statistical Analysis Plan

**Sample size and power.** All participants meeting study eligibility requirements received the CDSMP classes for 6 weeks. Participants from this pool were randomized to the treatment arm (with ITEC and electronic devices such as the home BP monitoring, weight scale, and physical activity tracker), and the control arm, with IT monitoring only. Our sample of  $n=45$  participants per arm ( $N=90$  in total), measured at baseline, and at 3-, 6-, and 9-months post CDSMP, has approximately 80% power (assuming 5 dropouts per arm) to detect an effect size of  $\sim 0.205$  or greater at the  $\alpha=0.05$  level of statistical significance, given a realistic range of simulated unstructured covariance matrices. Assuming an 11% rate of attrition, the enrollment target was set at 90 for both arms, which would yield a final sample of 80 participants, or 40 per arm.

**Statistical analysis.** A hierarchical, mixed-effects repeated measures design was used to analyze the primary and secondary outcomes of interest. This model, which allows for heterogeneous variances across time points, is preferred over a simple univariate model that requires compound symmetry (i.e., the correlation between a measurement at time  $T_i$  and any other measurement within the same patients at  $T_j$ , is equal for all  $i$  and  $j$ ). A mixed-effects model is more efficient for handling missing at random (MAR) data than, for example, a generalized estimating equations (GEE) repeated measures approach, which requires the more restrictive assumption that missing data are missing completely at random (MCAR). We performed a sensitivity analysis using both a GEE model and sequential application of the EM algorithm to impute missing data. Data from participants ( $n=7$ ) who dropped out of the study before their first post-CDSMP visit were not included in the analysis. However, baseline information for these participants were compared with participants who continued in the study.

When appropriate a constrained longitudinal data analysis (cLDA) model was used, assuming the same baseline mean for treatment and referent arms with missing baseline data. The cLDA model examines treatment differences over time. Coffman et al. (2016) cite the cLDA as the method of choice for longitudinal RCTs because it yields robust estimates of treatment effect differences under reasonable missing data assumptions.

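### The stated comparator, CDSMP plus IT alone, does not describe the control arm in months 1–3, so a month-3 arm difference is not the effect of coaching over IT

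*Combined protocol and SAP*

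**What the plan says.** Four places define the control condition as technology without coaching, with no limit in time:

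- Objective: the intervention is evaluated "compared to the CDSMP and interactive technology (IT) alone".
- Design: lower BP and better adherence are expected "compared to participants receiving the CDSMP and IT alone".
- Technology: "study participants were randomly assigned to either the treatment (ITEC) or the control arm (IT").
- Statistical Analysis Plan, sample size paragraph: "and the control arm, with IT monitoring only".

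Two places describe a staged control. In the Description of the Study, Step 1 gives the treatment arm monitoring with weekly coaching, "while the control arm will receive usual care with manual BP measurements monthly". Only from Step 2 do both arms have devices: "the treatment arm will receive electronic monitoring with ITEC biweekly, and the control arm will receive electronic monitoring only". Fitbit Monitoring agrees. It gives controls usual care with monthly manual BP and weight checks in months 1–3, hands over the devices after that, and has uncoached monitoring in months 4–9. It also ends the treatment arm's coaching after month 6, so that months 7–9 can show whether effects last.

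Month 3 is a measured visit in both arms: "Manual BP measurements were taken at baseline and then at month 3, 6, and 9". The other manual measures and the questionnaires follow the same schedule. The SAP analyses the outcomes in a mixed repeated-measures model, or a cLDA model where appropriate, over all visits.

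**The concern.** The aim asks what coaching adds to technology. At month 3 the control arm has neither technology nor coaching, so the contrast at that visit cannot answer that question. It estimates the whole package against no devices.

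BP control is the first aim, and BP is measured manually in both arms at month 3. If a month-3 difference, or a single effect averaged over visits, were reported under the aim as worded, coaching would be credited with a result that might come from the devices, from coaching, or from both. Nothing in the SAP warns that month 3 estimates a different contrast from months 6 and 9. A reader who has only the aim, the arm label or the SAP paragraph would have no reason to suspect it.

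**Working it through.** **1. Conditions side by side.** Usual care continues in both arms throughout, and both arms have had the CDSMP.

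| Months | Treatment arm | Control arm | Arms differ by |
|---|---|---|---|
| 1–3 | devices, weekly coaching | no devices; monthly manual BP and weight | devices and coaching |
| 4–6 | devices, biweekly coaching | devices, no coaching | coaching, and an earlier device start |
| 7–9 | devices, no coaching | devices, no coaching | past coaching, and an earlier device start |

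The Technology section says every participant was taught to use the tools after randomization. Fitbit Monitoring dates this for controls to after month 3, so no text gives controls devices sooner.

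**2. Nominal months of device use** at visits 3, 6 and 9, ignoring the two-week practice period that both arms had: treatment 3, 6, 9; control 0, 3, 6. The gap is 3 months at every visit.

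**3. What each contrast contains.** Assume additivity. Let d(m) be the effect of m months of uncoached device use against none, and let c3, c6, c9 be what coaching adds at each visit.

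- Month 3: d(3) + c3
- Month 6: d(6) − d(3) + c6
- Month 9: d(9) − d(6) + c9
- Equal-weight mean of the three: d(9)/3 + (c3 + c6 + c9)/3, because the d(3) and d(6) terms cancel

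Only month 3 carries a full device effect. At months 6 and 9 the device term is a difference between longer and shorter use. It is zero if the effect has levelled off by three months, and otherwise its sign is unknown. In the mean over visits a device term remains even if coaching does nothing.

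**4. Which outcomes.** The month-3 issue covers manual BP, weight/BMI, waist and questionnaires, including the Hill-Bone scale. Steps, calories and app-recorded medication come through Fitbit Plus, which controls did not yet have, so they allow no month-3 arm comparison.

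**5. The plan's own figures.** None bears on this point. The enrolment target reproduces (80/(1 − 0.11) = 89.9, rounded up to 90) and is not affected.

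**6. Illustration only.** The device effect and the SD are assumptions, not in the documents. Suppose coaching has no effect and devices alone lower systolic BP by δ at month 3, with n = 40 per arm and a two-sided t-test at 0.05. The noncentrality is (δ/SD)·√(n/2), with √20 = 4.472.

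| δ (mmHg) | SD | Noncentrality | Chance of significance |
|---|---|---|---|
| 0 | 12 | 0 | 5% |
| 2.5 | 12 | 0.208 × 4.472 = 0.93 | 15% |
| 5 | 12 | 0.417 × 4.472 = 1.86 | 45% |
| 5 | 10 | 0.500 × 4.472 = 2.24 | 60% |
| 5 | 15 | 0.333 × 4.472 = 1.49 | 31% |

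With the 83 left after the 7 early dropouts (90 − 7, split 41/42 assumed), the SD 12 figures are 15.5% for 2.5 mmHg and 47% for 5 mmHg. These are chances of detecting a real device effect with an unadjusted t-test, not with the planned model. The point does not depend on them.

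**The case against.** The strongest reply is that the harm is conditional. No sentence attributes a month-3 difference to coaching. The hypothesis concerns outcomes after the intervention, which means month 6 (coaching ends) or month 9 (the steps end), and at both visits controls were on uncoached IT. The SAP's only tests that name month 3 are paired tests within each arm, and its unpaired t-test names no visit. The staged control is described openly in two sections, and the arm label and SAP phrase can be taken as shorthand for the one technology component that controls receive.

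Much of this stands. The design is disclosed and legitimate, misattribution would occur only if a month-3 or pooled difference were reported under the aim, and the assumed power figures should not support the weight of the point.

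It does not remove the mismatch. The aim is not tied to a visit, the planned model includes month 3 for both arms, and the SAP does not say which visit or summary answers the aim. Following the wording as it stands would put a month-3 arm contrast under the wrong comparator.

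**Conclusion.** The stated comparator is wrong for months 1–3 and should be corrected. For the outcomes measured in both arms, the month-3 contrast is devices plus weekly coaching against neither, and any effect pooled over visits mixes it with the later contrasts. One of three post-baseline visits is affected directly. The conclusion rests on the text alone and needs no assumed effect size.

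Four stronger readings are tempting, and the documents do not support them:

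- *Months 6 and 9 are invalid or biased.* They are concurrent randomized comparisons with controls on uncoached IT. The earlier device start limits how they are described, but its effect may be zero and its direction is unknown.
- *The comparator was changed covertly.* The staged control is stated plainly in the Description of the Study and in Fitbit Monitoring.
- *The false-positive rate is inflated.* A device effect at month 3 would be a real difference between the arms; only its attribution to coaching would be wrong.
- *The SAP commits to a month-3 between-arm t-test.* Its month-3 t-tests are within arm. A month-3 arm contrast arises from the repeated-measures model.

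A secondary gap is that neither the hypothesis nor the unpaired t-test names a visit. Fitbit Monitoring stops coaching after month 6, while the Description of the Study says "The intervention will be divided into three steps" and counts the uncoached third step among them. That gap would exist whatever the controls received, and it adds no weight to the main point.

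**What to change.** 1. Reconcile the Objective, Design, Technology and SAP wording with the Description of the Study and Fitbit Monitoring. The comparator would read: CDSMP, with usual care continuing throughout as in both arms; in months 1–3, monthly manual BP and weight measures without devices; in months 4–9, IT without coaching. Because the text is retrospective, enter this as a dated clarification and leave the present wording of the aim visible.
2. Report visit-specific arm contrasts from the planned mixed or cLDA model under separate labels:
   - Month 3 (outcomes measured in both arms only): *IT plus weekly coaching versus no IT (usual care with monthly manual measures)*.
   - Month 6: *early IT with coaching versus delayed IT without coaching*.
   - Month 9: *the same arms three months after coaching ended (sustainability)*.
3. Base any statement about coaching over IT on months 6 and/or 9, with the earlier device start given as a limitation. Do not attribute a month-3 difference, or any summary that includes month 3, to coaching over IT.
4. As a secondary item, name the visit meant in the hypothesis and in the unpaired t-test.

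The cost is wording, plus labels on contrasts that the planned model already yields. No new data are needed and the sample size does not change. The price is a narrower claim about coaching alone than the aim now makes.

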## **Design**

The proposed project is a two-arm randomized controlled trial (RCT), repeated measures design. We hypothesized that participants who received the CDSMP and ITEC would have lower systolic/diastolic BP and better adherence to antihypertensive medication(s) and lifestyle recommendations post intervention compared to participants receiving the CDSMP and IT alone. Measurements were obtained over 9 months post CDSMP.

## **Methods**

### **Study Location**

The study took place in Charlotte, NC, and surrounding areas. The state of NC lies in the southeastern area of the United States, an area known as the Stroke Belt because of the high incidence of stroke and cardiovascular disease (CVD). The study sample consisted of 90 community-dwelling Black women who had a medical diagnosis of hypertension and meet the study criteria.

### **Study criteria**

Inclusion criteria included 1) self-identified as Black or African American; 2) 18-70 years of age; 3) English speaking; 4) had to live in the study community or surrounding area; 5) systolic blood pressure (BP) greater than or equal to 130 and/or diastolic BP greater than or equal to 80 at screening; 6) prescribed to take one or more antihypertensive medication(s); and 7) smartphone with provider network or Wi-Fi connectivity. Exclusion Criteria included 1) self-report of mental illness that interferes with daily functioning; 2) unable to be physically active; 3) current pregnancy; 4) plans to move from the study community during the project; 5) systolic BP greater than or equal to 160 and/or diastolic BP greater than or equal to 100; 6) uncontrolled diabetes ( $HbA1c >8.5$ ), hemodialysis, history of stroke (within past year with residual effects such as weakness, paralysis, and speech difficulty), cancer treatment (for spread of cancer to other places in the body), or heart attack (within the past year); and 7) concurrent participation in another research study and/or taken any Stanford self-management program.

## Recruitment

Women were recruited from Black church congregants that are known to have a high proportion of Black females, from businesses such as hair salons, Black sororities, and community events. Recruitment methods included flyers, announcements on websites using the flyer, presentations, follow-up phone calls, and face-to-face meetings with church leaders, congregants, business owners, sororities, and community members. Those interested in participating in the study were instructed to contact the research staff (PI or trained RAs) who are registered nurses, via telephone or email. The PI or RA conducted either a face to face or telephone screening interview. After an explanation of the study and answering questions, potential participants were (1) screened for inclusion/exclusion; (2) uncontrolled BP (systolic and/or diastolic greater than or equal to 130/80 but less than 160/100 mmHg; interviewees had their BP checked and reported the numbers when called for screening; BP was taken later to confirm eligibility before the consent form was signed and baseline data collected); and (3) ability to participate in physical activity using the Physical Activity Readiness Questionnaire (PAR-Q). Those who were eligible and agree to participate in the study were visited by the PI or RA at their home or another preferred private location. At that time, the participants BP was taken to confirm eligibility for the study. If the BP criteria was met, the participant provided informed consent and baseline data were obtained. If the BP criteria were not met, participants were thanked for their time and told that any collected information during the screening process would be discarded by shredding.

